### 8.6.2 Statistical Methods for Safety Analyses

Safety and tolerability will be assessed by clinical review of all relevant parameters including adverse events (AEs), laboratory tests, vital signs, and ECG measurements.

The analysis of safety results will follow a tiered approach (Table 13). The tiers differ with respect to the analyses that will be performed. Safety parameters or adverse events of special interest that are identified *a priori* constitute “Tier 1” safety endpoints that will be subject to inferential testing for statistical significance with p-values and 95% confidence intervals provided for between-group comparisons. For this protocol, there are no Tier 1 events. Other safety parameters will be considered Tier 2 or Tier 3. Tier 2 parameters will be assessed via point estimates with 95% confidence intervals provided for between-group comparisons; only point estimates by treatment group are provided for Tier 3 safety parameters.

Table 13 Analysis Strategy for Safety Parameters

Safety Tier	Safety Endpoint †	p-Value	95% CI for Treatment Comparison	Descriptive Statistics
Tier 2	Any AE		X	X
	Any Serious AE		X	X
	Any Drug-Related AE		X	X
	Any Serious and Drug-Related AE		X	X
	Discontinuation due to AE		X	X
	Specific AEs, SOCs, or PDLCs ‡ (incidence $\geq$ 4/1% of subjects in one of the treatment groups)		X	X
Tier 3	Specific AEs, SOCs or PDLCs ‡ (incidence $<$ 4/1% of subjects in all of the treatment groups)			X
	Change from Baseline Results (Labs, ECGs, Vital Signs)			X
† Adverse Event references refer to both Clinical and Laboratory AEs. ‡ Includes only those endpoints not pre-specified as Tier 1 or not already pre-specified as Tier-2 endpoints. Note: SOC=System Organ Class; PDLC=Pre-Defined Limit of Change; X= results will be provided.				

Adverse events (specific terms as well as system organ class terms) and predefined limits of change in laboratory, vital signs, and ECG parameters that are not pre-specified as Tier-1 endpoints will be classified as belonging to "Tier 2" or "Tier 3", based on the number of events observed. Membership in Tier 2 requires that at least 4 subjects in any treatment group exhibit the event; all other adverse events and predefined limits of change will belong to Tier 3.

The threshold of at least 4 events was chosen because the 95% confidence interval for the between-group difference in percent incidence will always include zero when treatment groups of equal size each have less than 4 events and thus would add little to the interpretation of potentially meaningful differences. Because many 95% confidence intervals may be provided without adjustment for multiplicity, the confidence intervals should be regarded as a helpful descriptive measure to be used in review, not a formal method for assessing the statistical significance of the between-group differences in adverse events and predefined limits of change.

Continuous measures such as changes from baseline in laboratory, vital signs, and ECG parameters will be considered Tier 3 safety parameters. Summary statistics for baseline, on-treatment, and change from baseline values will be provided by treatment group in table format. In addition, summary statistics for the difference between treatment groups will also be provided, along with nominal p-values for between-group differences. Mean change from baseline over time will be plotted with the corresponding standard errors.

The broad clinical and laboratory AE categories consisting of the percentage of subjects with any AE, a drug related AE, a serious AE, an AE which is both drug-related and serious, and who discontinued due to an AE will be considered Tier 2 endpoints. Ninety-five percent confidence intervals (Tier 2) will be provided for between-treatment differences in the

percentage of subjects with events; these analyses will be performed using the unstratified Miettinen and Nurminen method [57], an unconditional, asymptotic method.

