From the time of treatment allocation/randomization through 30 days following cessation of treatment or if the subject initiates new anticancer therapy, whichever is earlier, all adverse events must be reported by the investigator. Such events will be recorded at each examination on the Adverse Event case report forms/worksheets. The reporting timeframe for adverse events meeting any serious criteria is described in section 7.2.3.1. The investigator will make every attempt to follow all subjects with nonserious adverse events for outcome.

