
Sample Size and Power
	
The planned sample size was initially approximately 600 subjects. Japan will begin enrolling late in the enrollment period, and must meet a minimum enrollment regulatory requirement. Therefore enrollment from Japan may continue after enrollment in other countries ends. Total enrollment is now expected to be approximately 700 subjects. For PFS, the trial has ~98% power to demonstrate that pembrolizumab and epacadostat is superior to pembrolizumab and placebo at an overall 1-sided 1.25% alpha-level. For OS, the trial has ~79% power to demonstrate that pembrolizumab and epacadostat is superior to pembrolizumab and placebo at an initial overall 1-sided 1.25% alpha-level. Should the PFS comparison be statistically significant, the 1.25% alpha will be re-assigned to OS. Should the OS comparison be statistically significant, the 2.5% alpha will be re-assigned to ORR. Should the total alpha assigned to OS be 2.5%, the power to demonstrate improved OS with the combination will be about 86%. The treatment effect (true hazard rate) is assumed to be 0.65 for PFS and 0.70 for OS.

Based on review of IA2 data, the DMC recommended that all subjects stop oral therapy (epacadostat/placebo). After study completion, only selected analyses will be performed.

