**ORR analysis:** Should the definitive OS analysis be statistically significant, the definitive ORR analysis will be performed using the data available at IA2. Assuming the available alpha for the ORR comparison is 2.5% and an ORR of 35% for the pembrolizumab + placebo regimen, the study has ~97% power to detect an ORR rate for the combination regimen of 50%.

The above calculations are based on the following assumptions (in addition to the interim analysis plan in Section 8.7): 1) OS for the pembrolizumab + placebo regimen follows a distribution with a “cure” rate of 35%, with survival for the remaining 65% of patients following an exponential distribution with a median of 14 months; 2) PFS follows a distribution with a “cure” rate of 30%, with PFS for the remaining 70% of patients following an exponential distribution with a median of 4.75 months in the pembrolizumab + placebo regimen; 3) the hazard ratio for OS between the pembrolizumab + epacadostat combination and pembrolizumab + placebo is 0.7; 4) hazard ratio for PFS between the pembrolizumab + epacadostat combination and pembrolizumab + placebo is 0.65 and 5) an enrollment period of approximately 12 months. The sample size and power calculation were performed in the software R package gsDesign (see R code, Section 12.10).

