### **8.12 Extent of Exposure**

The extent of exposure will be summarized by treatment as duration of treatment in cycles. Dose intensity will also be summarized as appropriate.

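### Tier 2 adverse events are compared only as crude percentages although the plan expects time at risk to differ by arm: a spurious excess of up to about 7–10 points for common events, under 3 points for uncommon ones

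*Combined protocol and SAP*

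**What the plan says.** Section 8.6.2 has no Tier 1 safety endpoints, so the between-arm adverse event evidence is the Tier 2 set. For it the plan gives 95% intervals for differences in the "percentage of subjects with events; these analyses will be performed using the unstratified Miettinen and Nurminen method". Table 13 lists only that interval and descriptive statistics. Entry to Tier 2 is easy: "Membership in Tier 2 requires that at least 4 subjects in any treatment group exhibit the event". The section adds that, because many intervals are given without multiplicity adjustment, "the confidence intervals should be regarded as a helpful descriptive measure to be used in review".

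Exposure appears once, in Section 8.12: "The extent of exposure will be summarized by treatment as duration of treatment in cycles", with dose intensity where appropriate. Nothing links it to adverse event incidence.

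The observation window follows treatment. Sections 1.0 and 2.1 continue treatment until site-confirmed irRECIST progression or another stopping reason, up to 35 cycles of 21 days. Section 7.2 has adverse events reported "through 30 days following cessation of treatment or if the subject initiates new anticancer therapy, whichever is earlier". Serious events have a longer window in Section 7.2.3.1: 90 days after cessation, or 30 days if new anticancer therapy starts.

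Section 8.9.1 assumes for control that "PFS follows a distribution with a “cure” rate of 30%, with PFS for the remaining 70% of patients following an exponential distribution" with a 4.75-month median, and that the "hazard ratio for PFS between the pembrolizumab + epacadostat combination and pembrolizumab + placebo is 0.65".

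**The concern.** A crude percentage answers how many subjects had the event while observed. If one arm is observed longer, its percentage rises even when the monthly risk is the same. Here the length of observation is itself an outcome, and the trial is powered to show that it differs. Under the plan's own hypothesis the Tier 2 differences mix risk with duration and lean against epacadostat. If one arm instead stopped treatment earlier, for toxicity for example, crude percentages could understate its risk. Safety and tolerability of the two arms is a stated secondary objective, and the descriptive label in Section 8.6.2 deals with multiplicity. It does not deal with a shift in the point estimate.

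**Working it through.** **Plan's own figure.** The documents give no figure for this effect, so the first check is the PFS assumption behind it. With 420 events, HR 0.65 and one-sided alpha 0.0125:

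z = (√420 / 2) × |ln 0.65| − 2.241 = 10.247 × 0.4308 − 2.241 = 2.173, so power is 98.5%.

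The two-look version with exponential spending (parameter 0.75) gives boundary p-values 0.0053 and 0.0108 and power 98.4%. Both agree with the stated ~98%.

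**Time at risk.** PFS is used as a proxy for time on treatment.

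- λ = ln 2 / 4.75 = 0.1459 per month; cap T = 35 × 21 days = 735 days = 24.15 months.
- Control: S0(t) = 0.30 + 0.70·exp(−λt). Mean time to T = 0.30 × 24.15 + 0.70 × (1 − exp(−λT))/λ = 7.245 + 4.655 = 11.9 months.
- Epacadostat, HR on the whole curve: S1(t) = S0(t)^0.65, mean 15.0 months (+26%).
- Epacadostat, HR on the uncured 70% only: mean 13.9 months (+17%).

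**Crude incidence.** The documents give no adverse event hazard. Assume a constant hazard h, identical in both arms:

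incidence = ∫ h·exp(−ht)·S(t) dt, from 0 to T.

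Control example, h = 0.05: 0.30 × (1 − 0.299) + 0.70 × (0.05/0.1959) × (1 − 0.009) = 0.210 + 0.177 = 38.7%. The same integral with S1 gives 47.0%.

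The two percentage columns apply the HR to the whole curve, without the tail. Excesses are in points, from unrounded values.

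| h per month | Control % | Epacadostat % | Excess, whole curve | With 30-day tail | Excess, uncured only | With 30-day tail |
|---|---|---|---|---|---|---|
| 0.002 | 2.3 | 2.9 | 0.6 | 0.6 | 0.4 | 0.4 |
| 0.005 | 5.7 | 7.1 | 1.5 | 1.5 | 0.9 | 0.9 |
| 0.01 | 10.8 | 13.6 | 2.7 | 2.7 | 1.8 | 1.7 |
| 0.02 | 19.8 | 24.6 | 4.8 | 4.7 | 3.1 | 3.1 |
| 0.05 | 38.7 | 47.0 | 8.3 | 7.9 | 5.7 | 5.4 |
| 0.10 | 55.7 | 65.3 | 9.6 | 8.7 | 7.2 | 6.5 |
| 0.20 | 70.2 | 78.6 | 8.4 | 6.8 | 7.0 | 5.7 |
| 0.50 | 84.2 | 89.2 | 5.0 | 3.0 | 4.7 | 2.8 |
| 1.00 | 91.1 | 94.0 | 2.9 | 1.1 | 2.8 | 1.0 |

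The maxima over h are 9.6, 8.8 (tail), 7.4 (uncured only) and 6.5 (uncured only, tail). The excess reaches 3 points only for control incidence of about 12–91%, 13–90%, 19–91% and 21–90% respectively. A 12-month cap, as with an earlier data cut, lowers the whole-curve maximum to 7.1 and narrows the band to 19–91%.

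**Which rows fall in the band.** As illustration only, since populations and follow-up differ: the pembrolizumab monotherapy data in Section 4.3.2 show serious events 30.1%, drug-related events 76.8% and any event 97.3%. The first two are inside the band and the third is outside. Among 117 subjects on the combination (Section 4.3.3), seven terms reached 15%. Tier 2 entry at 4 subjects is 4/350 = 1.1%, so many specific terms would sit well below the band.

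**Early-onset events.** Suppose equal risk of 5–30%, confined to the first 1–3 months. Crude incidence then differs by only 0.1–1.2 points, but events per subject-month are lower on epacadostat, with a ratio of about 0.81–0.84. Example: 20% risk in month 1 only, so h = −ln 0.8 = 0.223. Subject-time is ∫ exp(−ht)·S(t) dt over month 1 plus 0.8 × ∫ S(t) dt from month 1 to T, which gives 9.61 v 12.13 months per subject. The rates are 0.1906/9.61 = 1.98 and 0.1938/12.13 = 1.60 per 100 subject-months, a ratio of 0.81. A constant rate alone therefore errs in the other direction for such events.

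**The case against.** A reader might infer that every Tier 2 row carries a 3–10 point bias. The documents do not support that. Tier 2 starts near 1% incidence, where the excess is a fraction of a point, and near-universal categories move little.

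A reader might also infer a flood of false safety signals. With 350 per arm and the whole-curve reading, the 95% interval would exclude zero in about 20% of trials at 1% per month and about 75% at 10% per month. Those figures use the intervals as tests, which Section 8.6.2 expressly says they are not.

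Other objections also stand. Central RECIST 1.1 PFS is an imperfect proxy: treatment ends on site-confirmed irRECIST progression, may continue past first progression, and also stops for toxicity or, optionally, after confirmed complete response. The 30-day window is current text. The amendment rationale says that reporting moved to the monotherapy standard after subjects had come off epacadostat, so it need not be the window in force during the randomised comparison. Applying 30 days to serious events would contradict Section 7.2.3.1. Section 2.1 reports no benefit of epacadostat at the interim review, so exposure was probably more alike than assumed. Exposure is also reported by arm, so an imbalance would be visible.

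What does not stand is that the descriptive label or the separate exposure summary resolves the matter. Neither shows how far a difference in percentages reflects duration, and similar PFS does not guarantee similar time on treatment.

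**Conclusion.** The gap is real but modest. The plan compares Tier 2 events only as crude percentages, while its own PFS hypothesis implies about 17–26% more time at risk on epacadostat. The resulting spurious excess is up to about 7–10 points for common events (about 6.5–9 with the 30-day tail). It is under 3 points below about 12% or above about 91% control incidence. These sizes rest on a constant, equal event hazard, on PFS as a proxy for exposure, and on the 35-cycle cap. They fall for early-onset events and approach zero if exposure was similar. It would go too far to call the planned safety analysis invalid: the crude percentages are legitimate descriptive results that lack a companion analysis.

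**What to change.** Keep the crude percentages and their Miettinen-Nurminen intervals. Add to Section 8.6.2 and Table 13 one supportive table for the broad Tier 2 categories and the common specific events:

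- First-event rate per arm (subjects with a first event divided by subject-months to first event or end of that row's reporting window), and the between-arm rate difference with 95% interval.
- Row-specific windows: 30 days after cessation for adverse events under Section 7.2; 90 days, or 30 days if new therapy starts, for serious events under Section 7.2.3.1. Count events and time over the same window.
- Beside it, time-to-first-event (cumulative incidence) estimates by arm, censored at the end of the window with death as a competing event. Treating the end of the window as a competing event would lead back to the crude percentage.

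The cost is one extra table with curves, from dates already collected. The constant rate is a simplification that can favour the longer-exposed arm for early-onset events, and censoring at the end of treatment may be informative, so the results are supportive only. Subjects are already unblinded and Section 8.1 foresees only selected further analyses, so the report should label the table as added after unblinding.

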### **8.6.3 Summaries of Baseline Characteristics, Demographics, and Other Analyses**

The comparability of the treatment groups for each relevant characteristic will be assessed by the use of tables and/or graphs. No statistical hypothesis tests will be performed on these characteristics. The number and percentage of subjects screened, randomized, the primary reasons for screening failure, and the primary reason for discontinuation will be displayed. Demographic variables, baseline characteristics, primary and secondary diagnoses, and prior and concomitant therapies will be summarized by treatment either by descriptive statistics or categorical tables.

## **8.7 Interim Analyses**

If the statistical criterion for success for one or more of the primary hypotheses is met at an interim analysis, a regulatory submission may be prepared while the trial continues, and the Clinical Study Report (CSR) will comprise all available data used to draw the conclusion in the decisive interim analysis. The remaining data obtained afterwards (from additional visits and close-out visits) will be reported in a subsequent CSR.

### **8.7.1 Efficacy Interim Analyses**

Three analyses (two interim and one final) are planned in this trial. [Table 14](#) provides the summary of the strategy and timing of the interim and final analyses. Accrual is expected to be completed prior to the first interim analysis. The final analysis of PFS will be performed at interim analysis 2 (IA2) scheduled to be performed at about 420 PFS events (about 24 months following the start of enrollment). The final analysis of OS will be performed at about 293 OS events (about 45 months following the start of enrollment).

Table 14 Summary of Interim Analysis Strategy

Analysis	Key endpoints	Targeted number of events at the time of analysis	Expected approximate timing of analysis (from study start)	Primary purpose of analysis
IA 1	PFS OS	Approximately 331 total PFS events. About 100 OS events are expected at IA1.	About 12 months	First interim analysis of PFS: demonstrate superiority of combination in PFS. First interim analysis of OS; Demonstrate superiority of combination in OS.
IA 2	PFS OS	Approximately 420 total PFS events. This is the final PFS analysis. About 200 OS events are expected at IA2.	About 24 months	Final analysis of PFS: demonstrate superiority of combination in PFS. Second interim look at OS; Demonstrate superiority of combination in OS.
Final	OS	Approximately 293 total OS events. This is the final OS analysis.	About 45 months	Final OS analysis: Demonstrate superiority of combination in OS.

Table 15 provides the details of the interim efficacy monitoring boundaries for PFS and OS.

Table 15 Decision Guidance at IA1 and IA2 PFS Analyses and Each OS Analysis under a Hypothetical Timings of Interim Analyses and Initially Assigned Alpha

Analysis	Targeted number of PFS events	One-sided PFS Efficacy boundary p-value	PFS observed hazard ratio	OS events	One-sided OS efficacy boundary p-value	OS observed hazard ratio
IA 1	~331	< 0.0053	< ~0.75	~100	< 0.0001	< ~0.46
IA 2 (Final PFS analysis)	~420	< 0.0108	< ~0.80	~200	< 0.0029	< ~0.68
Final OS Analysis				Targeted for ~293	< 0.0115	< ~0.77

The final analysis will take place when about 293 deaths have occurred between the pembrolizumab + epacadostat regimen and the pembrolizumab + placebo regimen, which is expected to occur ~45 months after study start. According to Table 15 the nominal alpha for the final OS testing is 0.0115 (one-sided) if no alpha re-use occurs. A nominal alpha < 0.0115 corresponds to the approximate observed hazard ratio for OS superiority < 0.77. The nominal alpha level for PFS and OS interim hypothesis testing will be re-calculated if the actual number of events available at the times of the interim analyses is different from those specified above. The nominal alpha level for OS interim hypothesis testing will be re-

calculated if alpha is transferred to the OS hypothesis testing following a significant difference seen in PFS. A 95% confidence interval will be provided for the hazard ratios to characterize the PFS and OS effects in case the superiority of the combination is not demonstrated.

ORR analysis: Should the definitive OS analysis be statistically significant at any interim or final analysis, the definitive ORR analysis will be performed using the data available at IA2.

### **8.7.2 Safety Interim Analyses**

The external Data Monitoring Committee (DMC) will perform ongoing review of the interim safety data from this trial, as described in Section 7.3.3.

## **8.8 Multiplicity**

The multiplicity strategy specified in this section will be applied to the overall ITT population for the testing of primary hypotheses. The overall type I error is strongly controlled at 2.5% (one-sided) for the multiple endpoints tested, as well as for the multiple analyses of overall survival planned using the methods of Maurer and Bretz [59], with 1.25% allocated up front to the PFS hypothesis and 1.25% allocated up front to the OS hypotheses. The trial is considered statistically positive if either PFS or OS is positive.

The superiority of PFS will be tested at 1.25% in this study. If the pembrolizumab + epacadostat combination regimen demonstrates superior PFS, the 0.0125 alpha will be re-assigned to the comparison of OS. Should the OS comparison be statistically significant, the alpha assigned to OS will be reassigned to the comparison of ORR.

A graphical display of the plans for re-allocation of alpha is displayed in [Figure 3](#).

[figure not shown]

Figure 3 Graphical Display of Testing Strategy

For the PFS and OS hypothesis, an exponential alpha-spending function (see Anderson and Clark [60]) with  $\nu=0.75$  (approximating an O'Brien-Fleming boundary) will be used. For PFS the cumulative alpha will be 1.25% unless OS and ORR are statistically significant, in which case the 1.25% alpha associated with OS will be reallocated to PFS and testing will be done at 2.5% alpha. For OS, the cumulative alpha will be 1.25% (if PFS superiority is not demonstrated) or 2.5% (if PFS superiority is demonstrated).

## 8.9 Sample Size and Power Calculations

### 8.9.1 Sample Size and Power for Efficacy Analyses

The study will randomize subjects in a 1:1 ratio into the pembrolizumab + epacadostat regimen and the pembrolizumab + placebo regimen. The overall sample size for this study was projected to be ~600 subjects (maximum enrollment 660). Enrollment, excluding Japan, was 662 subjects, and is expected to be a total of 700 subjects after enrollment in Japan is completed.

The study is event driven (i.e., number of subjects and follow-up time are subject to change but number of events is not) and will complete after approximately 293 deaths have been observed between the two treatments.

**PFS analysis:** The primary PFS analysis will be carried out at the second interim analysis, which occurs after about 420 PFS events have been observed, expected to occur about 24 months from the start of enrollment. An initial alpha of 1.25% will be allocated to the PFS analysis. If the number of PFS events is exactly as specified in [Table 15](#), the study has about 98% power to detect a 0.65:1.00 hazard ratio favoring combination therapy. A p-value less than 0.0108 for PFS corresponds to an approximate observed hazard ratio < 0.80.

**OS analyses:** OS efficacy analyses will be performed at the first and second interim analyses. The final analysis will be conducted when about 293 deaths have been observed. An initial alpha of 1.25% will be allocated to the OS analysis. If the comparison of PFS is not statistically significant, and the number of OS events is exactly as specified in [Table 15](#), the study has about 79% power to detect a 0.70 hazard. Details on the nominal alpha and the approximate efficacy boundary at each interim analysis are summarized in Section 8.2.9. The nominal alpha levels will be re-calculated based upon the actual observed number of deaths at each interim analysis using the alpha-spending function. If the comparison of PFS is statistically significant, the 1.25% allocated to the PFS comparison will be re-allocated to the OS comparison. If superiority of the combination is demonstrated for PFS, the OS comparison will be performed at an alpha of 2.5% and, if the final analysis is done at 293 OS events, the power to detect a true hazard ratio of 0.70 will be approximately 86%. If the accumulation of the final number of OS events (293) is substantially delayed from the estimated 45 months, an additional interim analysis may be added.

**ORR analysis:** Should the definitive OS analysis be statistically significant, the definitive ORR analysis will be performed using the data available at IA2. Assuming the available alpha for the ORR comparison is 2.5% and an ORR of 35% for the pembrolizumab + placebo regimen, the study has ~97% power to detect an ORR rate for the combination regimen of 50%.

The above calculations are based on the following assumptions (in addition to the interim analysis plan in Section 8.7): 1) OS for the pembrolizumab + placebo regimen follows a distribution with a “cure” rate of 35%, with survival for the remaining 65% of patients following an exponential distribution with a median of 14 months; 2) PFS follows a distribution with a “cure” rate of 30%, with PFS for the remaining 70% of patients following an exponential distribution with a median of 4.75 months in the pembrolizumab + placebo regimen; 3) the hazard ratio for OS between the pembrolizumab + epacadostat combination and pembrolizumab + placebo is 0.7; 4) hazard ratio for PFS between the pembrolizumab + epacadostat combination and pembrolizumab + placebo is 0.65 and 5) an enrollment period of approximately 12 months. The sample size and power calculation were performed in the software R package gsDesign (see R code, Section 12.10).

